- To assess the overall safety and tolerability of nivolumab and ipilimumab versus SBRT plus nivolumab and ipilimumab in subjects with metastatic Merkel cell carcinoma.
- To evaluate whether PD-L1 expression is a predictive biomarker for ORR.
- To evaluate the Health Related Quality of Life (HRQoL) as assessed by European Organisation for Research and Treatment of Cancer (EORTC) QLQ-C30.

Exploratory: See [Section 1.3.3](#) of the protocol.

Study Design:

This is a Phase 2, randomized, multi-institutional study of nivolumab and ipilimumab alone versus in combination with SBRT for subjects (≥ 18 years) with metastatic Merkel Cell Carcinoma. Approximately 50 subjects will be randomized 1:1 and stratified by prior immunotherapy exposure. Dose reductions will not be allowed.

Treatment Arms:

Randomized 1:1 [Arm A: Arm B]: Treatment until progression on either arm.

Arm A:

Nivolumab 240 mg IV over 30 min q2 weeks and Ipilimumab 1 mg/kg IV over 30 min q6 weeks until progression or unacceptable toxicity

Arm B:

Nivolumab 240 mg IV over 30 min q2 weeks and Ipilimumab 1 mg/kg IV over 30 min q6 weeks until progression or unacceptable toxicity

Radiation to be given at the start of week 2

- 8 Gy x3 doses in over ≤ 2 weeks

SBRT should begin the week following the first dose of nivolumab and ipilimumab. All sites other than skin should receive SBRT in consecutive days. Skin lesions can be treated every other day.

The number of lesions receiving SBRT will be at the treating physician's discretion based on anticipated toxicity. Larger or symptomatic lesions are of higher priority for SBRT. At least one target lesion will not receive SBRT, to evaluate ORR. The scatter radiation dose to this target lesion should be monitored if located less than 6cm from the irradiated lesions.

All subjects will be treated until progression of disease, unacceptable toxicity, or subject withdrawal of consent. Palliative radiation therapy will not be permitted while being treated under the protocol. The need for palliative radiation therapy will be considered progressive disease.

Study Population: Metastatic Merkel cell carcinoma subjects

Key Inclusion Criteria:

- At least 18 years of age
- ECOG PS < 2
- Active disease measurable by CT or MRI.
- Prior chemotherapy or immunotherapy will be allowed if new or persistent measurable site(s) of disease are present.
- Prior radiation therapy will be allowed if there is active measurable disease burden.

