6 RADIATION THERAPY

Metastatic lesions with the following distribution are eligible to be treated with SBRT on this protocol:

1 – 4 metastases distinct from the measurable target lesion that will not be irradiated to evaluate responses to the abscopal effect and immunotherapy. Larger lesions are given preference for SBRT to maximize tumor antigen release. The irradiated lesion will not be included in the calculations for measurable disease.

SBRT will be given Week 2 - 3, please see Section 5.5 and 6. SBRT should begin Week 2, and therefore, the radiation planning process should begin as the patient is registered for the study prior to randomization. SBRT for all metastases should be completed within 2 weeks of the first dose of SBRT. Not all metastases need to receive radiation therapy on the same day.

Most commercially available photon producing treatment units are allowed. As such, conventional linear accelerators, specialized linear accelerators with image guidance (e.g., Novalis, Trilogy, Synergy, Artiste, TrueBeam) are allowed. These units can be used with conformal dose delivery or IMRT. Specialized dose painting accelerators (e.g., Cyberknife, Gammaknife or Tomotherapy) are allowed provided they meet the technical specifications of the protocol and are used in a fashion that passes the credentialing required by the protocol. Conventional linear accelerators without add-on IGRT must have some other IGRT capability like CT-on-rails in the treatment room.

IGRT is required for this study. Either 3DCRT or IMRT (including VMAT) are all acceptable planning techniques. Planning techniques may differ for each lesion to be treated provided that the tumor motion is properly accounted for with each technique when the target or targets are in or near the thorax region.

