6.1 Dose Specification

6.1.1 Dose Fractionation

Patients will receive 24Gy in 3 fractions of radiation in 3 consecutive days for non-skin lesions. Skin lesions are allowed to be treated every other day. Simultaneous integrated boost or dose-painting will be allowed to meet normal tissue dose constraints. If dose-painting is utilized, we recommend V21Gy > 90% of GTV and V24Gy > 1cc. This dose is well below the standard dose fractionation employed by SBRT in various disease locations ranging from 30Gy to 45Gy in 3 fractions, which have been deemed safe on available evidence and/or expert consensus in each disease site. Therefore we do not anticipate treatment related toxicity.

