Less likely, but serious (<20%): Radiation-induced liver disease (RILD) (<5%). Classic RILD is a clinical diagnosis of anicteric ascites, hepatomegaly and elevation of alkaline phosphatase relative to other transaminases that may occur 2 weeks to 3 months following radiation to the Liver; non-classic RILD includes elevation of liver enzymes and/or any decline in liver function within 12 weeks from start of therapy (~20%). RILD can lead to liver failure that could lead to death. There is an increased risk of liver toxicity in patients with large tumors and in patients with pre-existing liver disease; permanent thrombocytopenia (<1%); this may lead to bleeding; kidney injury (<1%); this may lead to changes on imaging and more rarely the need for medication.

Spinal metastases

Radiation Myelitis

Given the proximity and position of spinal cord in relation to the radiosurgery target, every effort should be made to minimize the radiation dose to the spinal cord. Radiation myelitis is a subacute or chronic clinical syndrome after radiation. The symptoms may include paresthesia, sensory changes, and motor weakness including paralysis. There is no active treatment for radiation myelitis; therefore, it is

important to prevent any injury to the spinal cord. Corticosteroids are used when clinical symptoms develop.

Radiation Esophagitis

Patients with thoracic spine treatment will likely develop esophageal mucositis within the first 2 weeks. These symptoms subside with time; however, adequate symptomatic treatment including hydration is advised. There are no long-term adverse events reported with spine radiosurgery.

However, it is prudent to minimize the radiation spillage in the normal esophagus. The consequences of esophageal toxicity, e.g., swallowing difficulty, dysphagia, cough, dehydration, and fistula, should be documented.

Radiation Laryngitis or Pharyngitis

Patients with cervical spine treatment will likely develop laryngopharyngeal mucositis within the first 2 weeks. These symptoms subside with time; however, adequate symptomatic treatment including hydration is advised. No long-term laryngopharyngeal toxicity has been reported with spine radiosurgery. However, it is prudent to minimize the radiation spillage in the normal larynx and pharynx. The consequences of toxicity, e.g., swallowing difficulty, dysphagia, cough, dysphonia, dehydration, and fistula, should be documented.

Tracheal Injury

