Review of concomitant medications	x	x	x	x	x	x	
Pregnancy Test	x			x		x	Every 4 weeks \pm 1 week. Serum or Urine.
Laboratory Tests	x		x	x	x	x	Within 72 hrs prior to dosing/SBRT to include CBC w/differential, LFT's, BUN or serum urea level, creatinine, Ca, Mg, Na, K, Cl, LDH, Glucose, amylase, lipase, TSH (with reflexive Free T4/T3)
Exploratory Biomarker Assessments							
Plasma	x	x	x		x		Prior to dosing/SBRT
Peripheral Blood Mononuclear Cells (PBMCs)	x	x	x		x		Prior to dosing/SBRT
Efficacy Assessments							
Surveillance Assessments	Every 12 weeks (\pm 7 days) from first dose of study treatment through 12 months (until distant recurrence)						Clinical exam and/or CT scan of the involved disease sites and all known sites of resected disease and brain MRI (brain CT allowable if MRI is contraindicated or if there is no known history of resected brain lesions). Use same imaging method as was used at screening/baseline.
Study Drug							
Randomize	x						
Study Treatment	x	RT	x	x	x	x	First dose to be administered within 14 days of randomization. See Section 5.5.
Outcome Research							
EORTC-QLQ-C30	x				x		Prior to dosing. D1W1 should be completed after randomization but prior to dosing.
EQ5D (optional)	x				x		
WPAI:GH (optional)	x				x		
Health Care Resource Utilization (optional)	x				x		

Table 7.1-3: On-Treatment Assessments Week 11 - Week 21

Procedure	Wk11	Wk13	Wk15	Wk17	Wk19	Wk21	Notes
Safety Assessments							
Targeted Physical Examination	x	x	x	x	x	x	
Vital Signs	x	x	x	x	x	x	Including BP, HR, temperature
Oxygen saturation	x	x	x	x	x	x	By pulse oximetry prior to dosing
Weight and performance status	x	x	x	x	x	x	Within 72 hours of dosing
Adverse Events Assessment	Continuously						See Section 6.8. and Section 8
Review of concomitant medications	x	x	x	x	x	x	
Laboratory Tests	x	x	x	x	x	x	Within 72 hrs prior to dosing to include CBC w/differential, LFT's, BUN or serum urea level, creatinine, Ca, Mg, Na, K, Cl, LDH, Glucose, amylase, lipase, TSH (with reflexive Free T4 and T3)
Pregnancy Test		x		x		x	Every 4 weeks ± 1 week. Serum or Urine.
Exploratory Biomarker							
Plasma		x					Prior to dosing
Peripheral Blood Mononuclear Cells (PBMCs)		x					Prior to dosing
Efficacy Assessments							

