APPENDIX 5 EORTC QLQ-C30 (VER 3) FORM

We are interested in some things about you and your health. Please answer all of the questions yourself by circling the number that best applies to you. There are no "right" or "wrong" answers. The information that you provide will remain strictly confidential.

Please fill in your initials:
□□□□

Your birthdate (Day, Month, Year):
□□□□□□□□

Today's date (Day, Month, Year): 31
□□□□□□□□

	Not at All	A Little	Quite a Bit	Very Much
1. Do you have any trouble doing strenuous activities, like carrying a heavy shopping bag or a suitcase?	1	2	3	4
2. Do you have any trouble taking a long walk?	1	2	3	4
3. Do you have any trouble taking a short walk outside of the house?	1	2	3	4
4. Do you need to stay in bed or a chair during the day?	1	2	3	4
5. Do you need help with eating, dressing, washing yourself or using the toilet?	1	2	3	4

During the past week:	Not at All	A Little	Quite a Bit	Very Much
6. Were you limited in doing either your work or other daily activities?	1	2	3	4
7. Were you limited in pursuing your hobbies or other leisure time activities?	1	2	3	4
8. Were you short of breath?	1	2	3	4
9. Have you had pain?	1	2	3	4
10. Did you need to rest?	1	2	3	4
11. Have you had trouble sleeping?	1	2	3	4
12. Have you felt weak?	1	2	3	4
13. Have you lacked appetite?	1	2	3	4
14. Have you felt nauseated?	1	2	3	4
15. Have you vomited?	1	2	3	4

16. Have you been constipated? 1 2 3 4

During the past week:

	Not at All	A Little	Quite a Bit	Very Much
17. Have you had diarrhea?	1	2	3	4
18. Were you tired?	1	2	3	4
19. Did pain interfere with your daily activities?	1	2	3	4
20. Have you had difficulty in concentrating on things, like reading a newspaper or watching television?	1	2	3	4
21. Did you feel tense?	1	2	3	4
22. Did you worry?	1	2	3	4
23. Did you feel irritable?	1	2	3	4
24. Did you feel depressed?	1	2	3	4
25. Have you had difficulty remembering things?	1	2	3	4
26. Has your physical condition or medical treatment interfered with your family life?	1	2	3	4
27. Has your physical condition or medical treatment interfered with your social activities?	1	2	3	4
28. Has your physical condition or medical treatment caused you financial difficulties?	1	2	3	4

For the following questions please circle the number between 1 and 7 that best applies to you

29. How would you rate your overall health during the past week?

1 2 3 4 5 6 7

Very poor

Excellent

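### No QLQ-C30 is taken between Week 1 and Week 7, so patient-reported SBRT effects that clear within about 2-4 weeks are largely missed and Arm B's short-term burden may be understated

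*Combined protocol and SAP*

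**What the plan says.** **Schedule.** In Table 7.1-2 (Section 7.1) the QLQ-C30 row is marked at Weeks 1 and 7 only, with the note "Prior to dosing. D1W1 should be completed after randomization but prior to dosing". The later tables continue at Weeks 13, 19 and every six weeks to Week 49. There is no form at Weeks 2, 3, 5 or 9.

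**Recall.** In Appendix 5, items 6-28 stand under the heading "During the past week", and items 29 and 30 carry the same period in their wording ("How would you rate your overall health during the past week"). Items 1-5 have no recall heading.

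**SBRT timing.** The synopsis says "SBRT should begin the week following the first dose of nivolumab and ipilimumab". Section 6 says "SBRT will be given Week 2 - 3, please see Section 5.5 and 6" and "SBRT for all metastases should be completed within 2 weeks of the first dose of SBRT". Section 6.1.1 adds "Patients will receive 24Gy in 3 fractions of radiation in 3 consecutive days for non-skin lesions". Section 6.7 accepts a course lasting more than 2 but less than 3 weeks as a variation.

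**Expected effects.** Section 6.8 includes early effects: nausea and vomiting during therapy for liver and abdominal-pelvic sites, esophagitis that usually settles in days to a week or somewhat longer, and, for spine treatment, "Patients with thoracic spine treatment will likely develop esophageal mucositis within the first 2 weeks". The same section allows fatigue of up to 8 weeks for any treated site and places pneumonitis weeks to months after treatment.

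**Purpose and analysis.** Section 1.4.10 says the QLQ-C30 is to assess change in quality of life both during and after treatment in the study's arms. Section 9.2.2 defines the endpoint as mean change from baseline. Section 9.3.4 summarizes it descriptively by time point and arm and leaves between-arm analyses optional and exploratory.

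**The concern.** The planned drugs are the same in both arms, so SBRT is the one planned difference. It is a short course early in treatment, and several of the effects the protocol expects from it are early and short-lived. The only form before Week 7 is the pre-dose baseline, which precedes SBRT. For SBRT, the during-treatment part of the Section 1.4.10 aim is therefore not met by any form.

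At stake is how the HRQoL summaries are read. Similar Week 7 scores in the two arms could be taken to mean that adding SBRT cost patients little, when the weeks in which the arms differ most were not sampled. The blood biomarkers, by contrast, are drawn around SBRT, at Weeks 1, 2, 3 and 7.

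**Working it through.** The plan gives no figure of its own on this point, so the check is calendar arithmetic.

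**Inputs**
- First day of Week w = 7(w - 1) + 1. Week 2 starts on Day 8, Week 3 on Day 15, Week 5 on Day 29 and Week 7 on Day 43.
- Recall = the 7 days before the form (Appendix 5), with the form completed before dosing (Table 7.1-2).
- First fraction on Day 8 (synopsis; Section 6).
- Last fraction on Day 10 (three consecutive days, Section 6.1.1: 8 + 2), Day 21 (two weeks, Section 6: 8 + 13) or about Day 28 (accepted variation, Section 6.7: 8 + 20).
- Dosing visits may move by 2 days either way (Section 5.5.1).

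**Step 1: what the Week 7 form recalls.** 43 - 7 = 36 to 43 - 1 = 42, that is Days 36-42.

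**Step 2: gap from last fraction to first recalled day (36 minus last-fraction day)**

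| Last fraction | Gap, nominal visit | Gap, visit moved by 2 days |
|---|---|---|
| Day 10 | 36 - 10 = 26 days (3.7 weeks) | 24-28 days |
| Day 21 | 36 - 21 = 15 days (2.1 weeks) | 13-17 days |
| Day 28 | 36 - 28 = 8 days (1.1 weeks) | 6-10 days |

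A first fraction on the last day of Week 2 (Day 14) instead of Day 8 would shorten each nominal gap by 6 days, to 20, 9 and 2 days.

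**Step 3: coverage of Weeks 2-5 (Days 8-35, 28 days).** On nominal visit days, 0 of 28 days fall in a recall window. A form brought forward to Day 41 recalls Days 34-40 and so reaches 2 of 28.

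**Step 4: which effects fall in the gap.** Effects confined to the treatment days, such as nausea during therapy, are outside every recall window. So is esophagitis that settles within days to about a week of a course completed within the two-week rule and started on Day 8.

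**Step 5: which effects do not.** Fatigue lasting up to 8 weeks (56 days) could run to Day 10 + 56 = 66 or Day 21 + 56 = 77; counted from the first fraction, to Day 8 + 56 = 64. All lie beyond Day 42, so such fatigue can register at Week 7 through items 10, 12 and 18. Pneumonitis arising weeks to months after treatment can register at Week 7 or Week 13.

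**Step 6: effect of two added forms.** A Week 3 form (Day 15) recalls Days 8-14, and a Week 5 form (Day 29) recalls Days 22-28. Coverage of Weeks 2-5 rises from 0 to 7 + 7 = 14 of 28 days.

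**The case against.** The strongest reply has four parts.

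1. **Acute effects are not wholly lost.** A reader might infer that the schedule cannot record acute SBRT effects at all. Section 6.8 does not support that. Fatigue, the effect it names for every treated site, may last long enough to be recalled at Week 7. For spine-treatment mucositis it gives an onset but no duration. This stands and limits the point to effects that resolve quickly. Fatigue is only a partial rescue, however: 8 weeks is an upper limit, and for liver and abdominal-pelvic sites the section says fatigue generally goes once radiation is finished.

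2. **No formal comparison is biased.** Section 1.3.2 sets out to evaluate HRQoL, whereas PFS and OS are to be compared, and Section 9.3.4 makes between-arm analyses optional. A reader might infer that a finding of no difference is built in. It is not: later effects can still separate the arms, and no HRQoL test or decision rule is specified.

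3. **Tolerability is judged elsewhere.** A reader might infer that the tolerability conclusion would favour SBRT. Section 9.2.2 bases tolerability on adverse events, serious adverse events, deaths and laboratory abnormalities. Adverse events are assessed continuously, examination and performance status are scheduled at Weeks 2, 3 and 5, and an interim review looks for excess grade 3 or higher SBRT toxicity. This stands. Even so, adverse-event grading does not measure functioning or global quality of life, and Section 8 says patients should not be asked about specific events, so milder burden may go unreported.

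4. **The schedule is coherent.** Six-weekly forms match the ipilimumab visits, and the protocol expects little toxicity at this SBRT dose (Sections 1.5.4 and 6.1.1). That explains the choice, but it does not reconcile it with the Section 1.4.10 aim.

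**Conclusion.** The point holds in a limited form. The QLQ-C30 does not sample the SBRT period or, for a course started on Day 8 and completed within two weeks, about the first 2-4 weeks after it (15 to 26 days on nominal visits). If the course runs to Day 28, the unsampled time after SBRT falls to about 8 days, and a late start in Week 2 shortens it further. Short-lived patient-reported effects are therefore largely missed, and the HRQoL summaries may understate Arm B's short-term burden.

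The consequence is modest. HRQoL is a secondary, descriptive endpoint, persistent and subacute effects remain visible to it, and acute toxicity is captured as adverse events. The documents give no expected size of QLQ-C30 change after SBRT, so the understatement cannot be expressed in scale points.

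The conclusion rests on patients answering items 6-30 for the week before the form and on visits keeping to the schedule. Items 1-5 have no stated recall period, but no form is completed in the gap for them either. This is a low-cost improvement that brings the schedule into line with the protocol's own aim; it is not a flaw in the trial's main conclusions.

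**What to change.** Add the QLQ-C30 in both arms at the Week 3 and Week 5 visits, before dosing, in Table 7.1-2, and name these time points in the Section 9.3.4 summaries by arm. Both arms already attend these visits for dosing, laboratory tests and examination. A side benefit is that some patients who leave before Week 7 would then have the follow-up form that Section 9.3.4 requires for inclusion in the HRQoL analysis.

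The cost is two more 30-item forms per patient, a small added burden, with no new visits.

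If enrolment is too advanced for this to help, state in Section 9.3.4 and in the study report that the HRQoL data do not cover the SBRT period, and that similar Week 7 scores are not evidence of no acute burden.

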7.1.1 Retesting During Screening or Lead-in Period

Retesting of laboratory parameters and/or other assessments within any single Screening will be permitted (in addition to any parameters that require a confirmatory value).

Any new result will override the previous result (ie, the most current result prior to Randomization) and is the value by which study inclusion will be assessed, as it represents the subject's most current, clinical state.

Laboratory parameters and/or assessments that are included in Section 7. Screening Procedural Outline may be repeated in an effort to find all possible well-qualified subjects. Consultation with the Medical Monitor may be needed to identify whether repeat testing of any particular parameter is clinically relevant.

7.2 Study Materials

- NCI CTCAE version 4.0
- Nivolumab Investigator Brochure
- Ipilimumab Investigator Brochure
- Pharmacy binder
- Laboratory manuals for collection and handling of blood (including biomarker and immunogenicity) and tissue specimens
- Site manual for enrollment/randomization worksheets
- Manual for entry of local laboratory data
- Pregnancy Surveillance Forms
- PRO instruments.

7.3 Safety Assessments

At baseline, a medical history will be obtained to capture relevant underlying conditions. The baseline examinations should include weight, height, ECOG Performance Status, BP, HR, temperature and oxygen saturation by pulse oximetry and should be performed as noted in Table 5.1-1 Notes. Baseline signs and symptoms are those that are assessed within 14 days prior to randomization. Concomitant medications will be collected from within 14 days prior to randomization through the study treatment period and follow-up visits 1 and 2. During the Survival Follow-up visits subsequent only anti-cancer therapy will be collected.

Baseline local laboratory assessments should be done within 14 days prior to randomization to include: CBC w/differential, LFTs (ALT, AST, total bilirubin, alkaline phosphatase), BUN or serum urea level, creatinine, Ca, Mg, Na, K, Cl, LDH, glucose, amylase, lipase, TSH, Free T4, Free T3, and Hep B and C testing (HBV sAg, HCV RNA) (Table 5.1-1). Pregnancy testing for WOCBP (done locally) must be performed within 24 hours prior to the initial administration of study drug at baseline and then every 4 weeks (+/- 1 week) during the treatment phase.

Subjects will be evaluated for safety if they have received any study drug. Toxicity assessments will be continuous during the treatment phase. During the safety follow-up phase Table 5.1-7, toxicity assessments should be done in person. Once subjects reach the survival follow-up phase either in person or documented telephone calls to assess the subject's status are acceptable.

Adverse events and laboratory values will be graded according to the NCI CTCAE version 4.0.

On-study weight and ECOG Performance status and vital signs should be assessed on at each on-study visit. Vital signs should also be taken as per institutional standard of care prior to, during and after dosing. Oxygen saturation by pulse oximetry should be assessed at each on study visit prior to dosing. The start and stop time of the infusions should be documented. Physical examinations are to be performed as clinically indicated. If there are any new or worsening clinically significant changes since the last exam, report changes on the appropriate non-serious or serious adverse event page.

On study local laboratory assessments should be done within 72 hours of dosing to include; CBC w/differential, LFTs (ALT, AST, total bilirubin, alkaline phosphatase), BUN or serum urea level, creatinine, Ca, Mg, Na, K, Cl, LDH, glucose, amylase, lipase, TSH with reflexive Free T4, Free T3. Additional measures including non-study required laboratory tests should be performed as clinically indicated or to comply with local regulations. Laboratory toxicities (eg, suspected drug induced liver enzyme elevations) will be monitored during the follow-up phase via on site/local labs until all study drug related toxicities resolve, return to baseline or are deemed irreversible.

Oxygen saturation by pulse oximetry should be obtained prior to each dosing and at any time a subject has any new or worsening respiratory symptoms. Accurate recording and documentation of oxygen saturation at two different activity levels is important because drug-related pulmonary toxicity can present initially as lower than baseline oxygen saturation. A reading at rest and on exertion should be obtained at each time point. The extent of the exertion should be based on the judgment of the investigator, but should remain consistent for each individual subject throughout the study. If the subject's status changes, the investigator can alter the extent of exertion based on their medical judgment. If a subject shows changes on pulse oximetry or other pulmonary related signs (hypoxia, fever) or symptoms (eg, dyspnea, cough, fever) consistent with possible pulmonary adverse events, the subject should be immediately evaluated to rule out pulmonary toxicity. An algorithm for the management of suspected pulmonary toxicity can be found in the nivolumab Investigator's Brochure.

Some of the previously referred to assessments may not be captured as data in the eCRF. They are intended to be used as safety monitoring by the treating physician. Additional testing or assessments may be performed as clinically necessary or where required by institutional or local regulations.

7.3.1 *Imaging Assessment for the Study*

Any incidental findings of potential clinical relevance that are not directly associated with the objectives of the protocol should be evaluated and handled by the Study Investigator as per standard medical/clinical judgment.

